Alcohol has multiple biological effects on the nervous system which each represent potential targets for pharmacotherapy of alcohol use disorders. Animal studies indicate that alcohol induced generation of GABA_A receptor neuroactive steroid agonists mediate several of alcohol's effects. Pharmacologic blockade of neuroactive steroid production has been reported to reduce alcohol intake in animal models. Dutasteride, a widely used medication to treat benign prostatic hypertrophy is an irreversible inhibitor of 5-alpha reductase (5AR) enzymes required for the production of neuroactive steroids, and thus has potential as a pharmacologic treatment for alcohol use disorders in humans. In a recently completed placebo controlled study in humans of the effects of a single 4 mg dose of dutasteride given 2-4 days prior to a moderate dose of alcohol (0.8 gr/kg body weight) we found that while dutasteride has limited effects on subjective responses to a standard battery of alcohol effect questionnaires, it produced a significant reduction in drinking during the first two weeks following dutasteride, but not placebo medication treatments for subjects with a history of moderate drinking. The proposed study will extend these findings by examining the safety and efficacy of dutasteride for alcohol use disorders in human subjects by conducting a 12-week randomized placebo controlled trial of dutasteride for the reduction of alcohol use in male problem drinkers.

Aim 1. To examine the safety and efficacy of dutasteride in helping problem drinkers to reduce or stop drinking. 160 men with hazardous levels of alcohol use (≥ 24 standard drinks / week) will be randomly assigned to treatment with either dutasteride or placebo for 12-weeks. Alcohol use will be reported daily via an interactive voice response system. Biological markers (gamma glutamyl transferase, carbohydrate deficient transferin) will be used as secondary measures of change in alcohol use and a serum neuroactive steroid metabolite 3 α -androstaneadiol glucuronide will be used to monitor inhibition of 5 α -reductase enzyme activity by dutasteride. We hypothesize that 1 mg / day dutasteride will be well tolerated by heavy drinkers, will produce $\geq 85\%$ reduction in serum markers of 5 α -reductase enzyme activity and that compared with placebo will result in a greater reduction in the number of heavy drinking days and drinks per week.

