General Design: This study employs a parallel-groups design in which dutasteride is compared with placebo to evaluate its safety and efficacy in reducing the likelihood of drinking and of heavy drinking by problem drinkers. The study will be conducted in the UCHC Department of Psychiatry Clinical Research & Evaluation Unit (CREU) and the Clinical Research Center (CRC). Random assignment to treatment group and double-blind conditions will be maintained throughout the study. The study will be conducted in three consecutive phases: a 1 to 2 week pre-treatment assessment period, a 12-week treatment period, and a 6-month post-treatment follow-up period. Patients will be provided medical management including brief counseling (adapted from Pettinati et al. 2004) at each treatment visit. Daily reports will limit retrospection bias during the treatment period. Objective laboratory data (serum GGT and %dCDT) will be used to further corroborate patient reports. Data obtained during the post-treatment follow-up period will make it possible to evaluate the durability of treatment effects beyond the period of active treatment.

Patients: Male drinkers who want to reduce or stop drinking will be recruited using advertisements in local media (including text ads in newspapers and weekly community circulars, radio ads on local radio stations, web ads on internet sites and web postings on community message boards), by posting/distributing recruitment materials at area Colleges and Universities, and in community settings with public posting areas (such as hospitals, town halls, public libraries, YMCA, health fairs/organizations), and by referral from UCHC medical clinics where screening for alcohol use problems using the NIAAA Screening, Brief Intervention, and Referral for Treatment (SBIRT) protocol

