breast tissue (0.5% vs. 0.2%). In other clinical studies, daily doses of 5 mg (i.e., 5 times the daily dose in the current proposed study) were administered to 60 subjects for 6 months with no adverse effects beyond those seen at the more commonly used daily dose of 0.5 mg. In studies of normal volunteers, doses of up to 40 mg daily of dutasteride for 7 days have been administered without significant adverse effects. Dutasteride is not currently FDA approved for use in women due to the potential risk of a specific birth defect (reduced size of male external genitalia).

C.3.b. Placebo drug will consist of lactose powder formulated by the Research Pharmacy Service in gelatin capsules indistinguishable from the capsules containing dutasteride.

C.3.c. Medication Randomization and Drug Accountability: The UCHC Research Pharmacy staff will be responsible for medication randomization and dispensing. The Research Pharmacy will enter randomization variables (age, AKR1C3 genotype, frequency of heavy drinking days for the 90-day period prior to screening, number of DSM-IV AD criteria, use of medication for treatment of co-morbid psychiatric condition, and drinks per drinking day from baseline 90-day TLFB) into an urn randomization program and provide to study staff a supply of study drug, as assigned. Although we will monitor capsule counts at each treatment visit, our primary measure of medication adherence will be daily IVR reports (section D.6.b.2). A daily diary method has been shown to yield results that are comparable to those obtained with electronic monitoring ($r = .91$) (Feinn et al. 2003).

C.4. Study Visits:

C.4.a. Visit 1 (Screening Visit): Prior to informed consent, subjects will have a breath alcohol (BrAC) measurement to validate sobriety. Following completion of informed consent, a brief medical and psychiatric history will be obtained by a study research assistant or nurse. Blood and urine samples will be taken for routine clinical laboratory evaluations, drug screening, DNA extraction and measurement of serum outcome measures GGT, %dCDT, the neuroactive steroid metabolite 3α -diolG and testosterone (to monitor for any unexpected negative effects of dutasteride on testosterone in heavy drinkers). Relevant portions of the Structured Clinical Interview for DSM-IV (SCID-I) will be administered by a research assistant to screen out subjects with major mental illness or dependence on other than alcohol or tobacco.

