C.4.b. Visit 2 (Baseline Visit): 7-14 days after the screening visit, eligible subjects will return for a baseline visit where subjects will be trained to record their mood, desire to drink, self-efficacy and daily drinking using the IVR system and a physical examination will be performed by a study physician or APRN and any medication questions reviewed. Subjects will be instructed in use of study medication and given their initial 4 mg dutasteride or placebo dose and instructed to take two capsules (1 mg) daily at home for the remainder of the 12-week treatment period. Subjects will receive study medication for home use at the baseline and at each follow-up visit. At the baseline visit subjects will receive a one-week back-up supply of medication for use in case of lost capsule or need to reschedule bi-weekly follow-up visits. Subjects will be asked to bring unused medication to each follow-up visit for monitoring medication use. The UCHC research pharmacy will randomly assign subjects to dutasteride or placebo using an urn randomization to balance subjects on AKR1C3 genotype, age and baseline alcohol use. Medication will be delivered or picked up from UConn Health IDS pharmacy for distribution to patients during IDS office hours (M-F 7:30am-4pm). For IDS off-hour appointments, medication may be obtained from IDS pharmacy and kept with study staff in a locked cabinet in a locked office in preparation for that appointment. In case a patient has a last minute cancellation or is a no-show, medication can be kept with study staff until the end of the business week. If the product is not distributed to the patient during that time, it will be returned to pharmacy.

C.4.c. Bi-weekly Clinic Visits 3 - 8: A brief Timeline Follow-Back Interview will be performed to track participants' daily alcohol consumption to augment IVR reports of alcohol use (see section D.9.a.2) and a trained research staff member will deliver the medical management intervention. Blood samples for study outcome measures (GGT, %dCDT, 3α -diolG, and testosterone) will be obtained at visits 5 and 8 (mid-point and end of treatment). We chose biweekly medication monitoring visits during the treatment period in order to optimize tolerability and thereby enhance treatment retention.

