At the end of treatment week 12 (visit 8), subjects will complete a packet of questionnaires and be interviewed by research staff concerning their alcohol consumption and alcohol-related symptomatology (using the Alcohol section of the SCID-I, modified to ask about the past 30 days). Subjects will be compensated \$50 for this end-of-treatment visit. Subjects requesting additional treatment for alcohol problems will be referred to local treatment centers. For subjects who withdraw early and do not wish to continue with study visits/procedures, all end-of-treatment procedures will be administered at the time of withdrawal. Such subjects will also be invited to participate in-person or by telephone to provide Timeline Followback data at 2, 4, and 6-months post-treatment.

C.4.d. Visit 9, 10, and 11 (Post-treatment Assessment Visits): To evaluate the durability of treatment effects, patients will return to the clinic for post-treatment assessments 2,4, and 6-months after completion (or for early terminators, scheduled completion) of treatment. We will attempt to reach all subjects directly or via their locator. At this visit, the subject will complete the self-report packet of questionnaires and will be interviewed by the research staff. Blood samples for measurement of serum GGT, %dCDT and 3 α -diolG will be obtained. Subjects will be paid \$50 for the two and four month post treatment visit and \$75 for the six month post-treatment assessment visits. Subjects will be eligible to request drug assignment information after their 6-month post-treatment assessment.

C.5. Medical Management: The physician will meet with the subject at the beginning of treatment and will consult at least weekly with the study staff to monitor potential study related side effects and adverse event occurrence. The physician will evaluate the subject should severe or persistent adverse effects occur. At each treatment visit (2-7) subjects will receive brief counseling as part of medical management, which is described in detail below.

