C.8.a.1. Safety: Safety will be analyzed using categorical outcomes, defined by the type and severity of adverse effects. Summary measures of adverse events (AEs) will be developed by organ system from the adverse event checklist and will be compared for patients receiving dutasteride or placebo using χ^2 analysis. Comparisons will be conducted on 1) the number of patients in each of the two groups who report AEs, 2) the number of patients in each of the two groups who report moderate-to-severe AEs, and 3) the number of patients in each group who discontinue treatment due to AEs. Individual AEs that occur in $\geq 5\%$ of patients in either medication condition will be examined using χ^2 analysis.

C.8.a.2. Efficacy: An important initial consideration will be to identify baseline differences between groups that may have occurred despite the use of urn randomization. The distribution of outcome data will also be examined prior to analysis, to determine the need for transformation and whether parametric analytic methods can be utilized. Successful outcome will be defined in terms of three primary dependent measures: SDs/week, HDDs/week, % of subjects with no HDDs, and % of subjects with non-hazardous drinking (no HDDs and SDs/week <15). Patients will be followed irrespective of whether they continue to receive treatment, so that analysis of both primary drinking measures and secondary outcomes will include all data available for the 12-week treatment period. Data for analyses of drinking outcomes during the 12-week treatment period will come from the daily IVR reports (missing IVR report days which will be coded as the larger of either 5 standard drinks (i.e. a HDD) or the IVR average daily use for the week reporting interval). Analysis of drinking for the 6-month follow-up period will be based on TLFB data collected at each follow-up visit. Secondary outcomes will include mean daily alcohol consumption, %dCDT levels (change relative to baseline), and severity of alcohol-related problems (as measured on the SIP and number of DSM-IV AD criteria).

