Efficacy analyses will be performed using linear mixed models implemented in SPSS. Medication group will be treated as a factor and treatment week as a continuous covariate. An interaction term between medication group and week will be used to evaluate the efficacy of dutasteride compared to placebo in reducing drinking behavior over time. Pretreatment drinking will be controlled for using TLFB drinking data for the month prior to screening as a covariate. Treatment goal (stop vs. reduce drinking) will also be included as baseline covariate. The robustness of results will be evaluated by running the model under three different conditions: 1) all provided information, 2) only completers, and 3) imputation where missing days are coded as HDDs for subjects who fail to complete treatment.

For aim 3, analysis of drinking outcome variables will be repeated by including genotype at the *AKR1C3* rs12529 polymorphism as an additional between-subject factor.

C.8.a.3 Examination of daily measures.

Multilevel models will be used to examine the relations among daily measures of mood, daily event triggers and the frequency of drinking and of heavy drinking (level 1 measures) and their moderation by medication (level 2 measure). To examine how the within-person processes vary across individuals (i.e., cross-level medication interactions), the level 1 parameters are considered as outcomes in the level 2 model. Of specific interest is how the level 1 slopes (e.g., the associations between mood or daily event triggers and heavy drinking) vary as a function of experimental condition (dutasteride vs. placebo). Control variables (baseline heavy drinking, depression symptom score, baseline AD symptom severity) will also be included in level 2 predictive models. The utility of each level 2 predictor will be determined by the significance tests of the level 2 partial regression slopes.

C.8.b. Sample size considerations:

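### GGT and %dCDT are both promised and drawn as objective secondary measures of drinking, but C.8.a.2 gives GGT no analysis and names no adjustment for either marker's own screening value.

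*Combined protocol and SAP*

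**What the plan says.** Aim 1 names two serum markers: "Biological markers (gamma glutamyl transferase, carbohydrate deficient transferin) will be used as secondary measures of change in alcohol use". The General Design in C.2 gives them a purpose: "Objective laboratory data (serum GGT and %dCDT) will be used to further corroborate patient reports".

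The samples are planned throughout. C.4.a (Visit 1) takes blood for "measurement of serum outcome measures GGT, %dCDT, the neuroactive steroid metabolite" and testosterone. C.4.c repeats the outcome bloods at visits 5 and 8, which Table 1 places at weeks 6 and 12. For the post-treatment visits C.4.d states: "Blood samples for measurement of serum GGT, %dCDT and 3 α -diolG will be obtained".

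The analysis section is narrower. C.8.a.2 states: "Secondary outcomes will include mean daily alcohol consumption, %dCDT levels (change relative to baseline), and severity of alcohol-related problems". GGT does not appear in C.8.

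The same section says "Efficacy analyses will be performed using linear mixed models implemented in SPSS", with medication group, week as a continuous covariate, and their interaction as the evaluation of efficacy. On baseline adjustment it says "Pretreatment drinking will be controlled for using TLFB drinking data for the month prior to screening as a covariate", and it adds treatment goal. No marker's screening value is named as a covariate.

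**The concern.** All the drinking outcomes are self-reported, and C.6.b.5 itself discusses the validity of those reports. GGT and %dCDT are the trial's objective evidence on drinking, so how they are analysed decides how much corroboration they can give.

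Two things are missing. GGT has no stated scale, time point, contrast or test, although it is promised in Aim 1 and drawn at every outcome visit. For %dCDT, the change from baseline is named but the model is not. If the drinking model is carried over unchanged, the named test is a slope over two on-treatment visits. An effect that is fully present by week 6 and then constant would not show in it. If a difference in level is intended instead, a change score without the marker's own baseline in the model gives up precision that data already collected could supply.

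**Working it through.** **1. The plan's own figure.** C.8.b gives 80 per group, d = 0.45, alpha 0.05 and 80% power. Sidedness is not stated. Two-sided: power = Φ(0.45·√(80/2) − 1.96) = Φ(2.846 − 1.960) = Φ(0.886) = 0.81. The t-test version also gives 0.81, while one-sided would give 0.885. The figure reproduces as two-sided. There is no separate calculation for the markers.

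**2. If the group-by-week interaction is the marker test.** Let X be the screening value and Y6, Y12 the on-treatment values. The between-visit difference in change is (Y12 − X) − (Y6 − X) = Y12 − Y6. X cancels, so with complete data own-baseline adjustment cannot alter the interaction. A simulation of 300 trials (80 per arm, correlation 0.5, random-intercept model) agreed. The two interaction estimates were the same to rounding error, with a standard error of 0.0264 for both.

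**3. If a between-arm difference in level is the marker test.** Take one on-treatment value, screening SD = 1, on-treatment SD = k and correlation r.
- Change-score variance: 1 + k² − 2rk.
- Variance adjusted for own baseline: k²(1 − r²).
- Difference: (1 − rk)², which is never negative.

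With k = 1 these become 2(1 − r) and 1 − r², and their ratio is (1 + r)/2. The value of r is an assumption, because the documents give none. Power below is for 80 per arm and a difference of 0.45 marker SD, two-sided 0.05. This is illustrative, since the plan states no marker effect.

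| r | change variance | adjusted variance | reduction | power, change | power, adjusted |
|---|---|---|---|---|---|
| 0.3 | 1.40 | 0.91 | 35% | 0.67 | 0.85 |
| 0.5 | 1.00 | 0.75 | 25% | 0.81 | 0.91 |
| 0.7 | 0.60 | 0.51 | 15% | 0.96 | 0.98 |
| 0.9 | 0.20 | 0.19 | 5% | 1.00 | 1.00 |

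**4. Does TLFB adjustment stand in for the marker's own baseline?** Suppose TLFB drinking correlates t with the screening marker and s with the on-treatment marker. The change score adjusted for TLFB then has variance 2(1 − r) − (s − t)². At r = 0.5:
- t = s = 0.3 (assumed) leaves it at 1.00, so nothing is gained.
- t = 0.4, s = 0.2 (assumed) gives 1.00 − 0.04 = 0.96, and power rises only from 0.81 to 0.83.

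**5. Chance imbalance at screening.** The urn variables in C.3.c include no serum marker. With 80 per arm the screening difference has SD √(2/80) = 0.158 marker SD, a 95% range of ±1.96 × 0.158 = ±0.31. A change score passes −(1 − r) times that difference into the estimated effect. At the edge of the range this is 0.22 SD at r = 0.3, 0.15 at 0.5, 0.09 at 0.7 and 0.03 at 0.9. In 20,000 simulated trials at r = 0.5 with t = s = 0.3, the TLFB-adjusted change estimate moved −0.51 per unit of imbalance. With own-baseline adjustment it moved −0.01. Standard errors were 0.160 and 0.136.

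**The case against.** The strongest reply is that the precision loss does not exist for the one test C.8.a.2 names. Step 2 shows that this is right for the interaction over weeks 6 and 12. The gain appears only once the estimand is a difference in level, so the fix has to state that estimand.

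A reader might infer that %dCDT is to be adjusted for reported drinking in place of its own baseline. The text does not say so. The model is worded around drinking behaviour and never names the markers, so TLFB adjustment of %dCDT is an inference. What holds on either reading is that no own-baseline adjustment is named.

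A reader might also infer bias from regression to the mean. That does not follow. The change score uses the screening value by subtraction, and regression to the mean acts on both randomised arms alike, so the contrast is unbiased over randomisations. Nor do the documents say that the change is on the raw scale: C.8.a.2 already plans to examine distributions and consider transformation. It also plans to look for baseline group differences, but states no adjustment that would follow.

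On GGT, Aim 1 does prespecify it as a secondary measure, and the wording in C.8.a.2 does not claim a complete list. The documents therefore do not show that GGT was dropped or that selective reporting is intended. What stands is that its analysis is unwritten and so remains open until the data are seen.

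Finally, these are not the trial's only objective outcomes. 3α-diolG is measured too, but it tracks enzyme inhibition rather than drinking.

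**Conclusion.** The point holds for secondary outcomes, as a free improvement. GGT is promised and sampled but has no analysis. The model for %dCDT is not tied to the marker, and neither marker's own screening value is named as a covariate.

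For a between-arm difference in level, own-baseline adjustment has a variance no larger than that of the change score at any correlation. The size of the gain rests on an assumed r, equal variances and a single visit: about 35% less variance at r = 0.3, falling to 5% at 0.9. A single headline figure, such as a fixed percentage of extra men, would claim more than the documents allow. Nothing here touches the primary drinking outcomes or the stated sample size, which reproduces.

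**What to change.** In C.8.a.2:
- List both %dCDT and GGT as secondary outcomes.
- Analyse each as the between-arm difference in level at weeks 6 and 12, in a mixed model with that marker's own screening value as covariate. Use the log scale if the planned distribution check shows skew.
- Report both markers with 95% confidence intervals, whatever the result.

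The sponsor may keep change from baseline as the outcome, because with the screening value in the model the estimated level difference is the same.

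While editing, align C.6.a, which speaks of two follow-up visits for these bloods, with C.4.d and Table 1, which give three.

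The cost is wording only: every sample and assay is already planned.

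### The efficacy model specifies no covariate-by-week term, so the planned adjustment for pretreatment drinking and treatment goal hardly reaches the medication-by-week test

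*Combined protocol and SAP*

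**What the plan says.** Section C.8.a.2 of the combined protocol and SAP sets out the efficacy model in five steps.

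- Model: "Efficacy analyses will be performed using linear mixed models implemented in SPSS".
- Time: "Medication group will be treated as a factor and treatment week as a continuous covariate".
- Test: "An interaction term between medication group and week will be used to evaluate the efficacy of dutasteride compared to placebo".
- Baseline drinking: "Pretreatment drinking will be controlled for using TLFB drinking data for the month prior to screening as a covariate".
- Goal: "Treatment goal (stop vs. reduce drinking) will also be included as baseline covariate".

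Medication by week is the only interaction named for the main efficacy model. The random effects and covariance structure are not given.

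Baseline drinking is also handled in the design. The urn variables in C.3.c include "frequency of heavy drinking days for the 90-day period prior to screening, number of DSM-IV AD criteria" and drinks per drinking day. C.4.b gives the purpose as "urn randomization to balance subjects on AKR1C3 genotype, age and baseline alcohol use". Treatment goal appears in neither list. C.8.a.2 opens with a step to "identify baseline differences between groups that may have occurred despite the use of urn randomization", but does not say what follows for the model if a difference is found.

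**The concern.** The tested quantity is a difference between arms in linear slope over the treatment weeks. Pretreatment drinking and treatment goal are constant within a man. Entered as main effects, they raise or lower his whole profile and leave its slope alone. The statement that pretreatment drinking is controlled for is then true of the level of drinking but has almost no content for the named test.

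Slopes may well depend on both covariates. A man who starts at a high intake has further to fall, and a man who wants to stop may fall faster than one who wants to cut down. If so, two things are at stake: precision that could be had from data already collected, and protection against chance imbalance, above all in treatment goal, which the urn does not balance.

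Precision is not in surplus here. Section C.8.b powers the trial for d = 0.45 but cites observed effects of 0.37 and 0.3.

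**Working it through.** **1. The plan's own figure.** Inputs from C.8.b: 80 per arm, d = 0.45, alpha 0.05 (two-sided assumed; the plan does not say). Power = Φ(d·√(n/2) − 1.96) = Φ(0.45 × √40 − 1.96) = Φ(0.886) = 81.2%, or 80.8% with the t distribution. The stated 80% is reproduced. Expected non-completion is 16/176 = 9.1%.

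**2. Which reading of the covariates?** The text neither states nor excludes covariate-by-week terms. Two internal signs favor main effects. The pilot mixed model in C.1.c reports baseline drinking as a main effect. For the daily measures, C.8.a.3 explicitly makes the within-person slopes outcomes and places baseline heavy drinking among their predictors; the efficacy paragraph has nothing similar.

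**3. Algebra with complete weeks.** For weeks t = 1 to 12 with mean 6.5, a man's fitted slope is Σ(t − 6.5)·y(t) / Σ(t − 6.5)². A main-effect term c·x adds the same constant to every y(t), and so adds c·x·Σ(t − 6.5) = 0 to the numerator. With complete data and a random intercept, with or without a random slope, medication by week is the difference in mean slopes. The covariate drops out.

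**4. Numerical check, including dropout.** Simulation: 12 weekly values, random intercept and slope with known covariance, 25 data sets per scenario. Assumed, not from the documents: the variance components, a slope change of −0.02 per baseline drink per week, and a deliberately large arm imbalance of 5 drinks per week. The shift is the change in the medication-by-week estimate when both main effects are added.

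| Weekly data | Mean absolute shift | Largest shift | Standard error | Mean shift / SE |
|---|---|---|---|---|
| Complete | below 1e-14 | below 1e-14 | 0.154 | 0% |
| 9% random dropout | 0.0046 | 0.010 | 0.151 | 3% |
| 9% dropout, dependent on early drinking | 0.0069 | 0.023 | 0.153 | 5% |
| 30% base rate, dependent on early drinking | 0.0096 | 0.030 | 0.168 | 6% |

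With complete data the standard error was 0.1539 with and without the main effects. A random-intercept REML fit to one complete data set gave −0.12946 (SE 0.11455) both ways. Random-slope REML fits had convergence warnings, and their standard errors are not used.

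**5. Terms that do reach the test.** In the complete-data scenario, adding both covariate-by-week terms moved the estimate by 0.084 on average, or 0.084/0.154 = 0.55 SE. This shows that these terms act on the tested quantity. Its size reflects the assumed imbalance and slope dependence and is not a forecast.

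**6. Precision.** Let R² be the share of the between-patient variance of fitted slopes that the covariates explain. Power = Φ(d·√40/√(1 − R²) − 1.96), with d in units of the unadjusted slope standard deviation.

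| Assumed R² | Power at d = 0.45 | d = 0.37 | d = 0.30 |
|---|---|---|---|
| 0 | 81.2% | 65% | 48% |
| 0.05 | 83.1% | | |
| 0.10 | 85.1% | 69% | 52% |
| 0.20 | 88.9% | 74% | 56% |
| 0.30 | 92.5% | | |

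**7. Room for imbalance in goal.** The pilot split in C.1.c was 73% reduce and 27% stop. Without balancing, one standard error of the difference between arms is √(0.27 × 0.73 × 2/80) = 0.070, or 7 percentage points.

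**The case against.** A reader might infer that the efficacy test is not controlled for baseline at all. The documents do not support that. The urn balances heavy-drinking-day frequency and drinks per drinking day, a within-man slope already removes stable differences in level, and a check for residual imbalance is planned. What stays unadjusted is any dependence of the slope itself on baseline drinking or goal.

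Other objections also carry weight:

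- **Validity.** Randomization keeps the unadjusted slope test valid, and chance imbalance is already reflected in its standard error. In a simulation with a proportional fall, the type I error was 4.8%. This is not a bias.
- **Complete data.** The exact result needs complete weeks. C.8.a.2 fills missing report days, but it also plans a run on all provided information and lists coding of missing days for non-completers as a separate run. The weekly average used in the fill does not exist in a week without reports. The shift under dropout is therefore small rather than zero.
- **Scale.** The plan allows transformation. In a simulation with a fall proportional to baseline, baseline explained 11% of slope variance on the raw scale and 0.6% on the log scale, which is chance level (1/159). The gain could vanish for baseline drinking.
- **Size of a spurious difference.** It is tempting to multiply the pilot's 39% placebo fall by a chance imbalance in baseline. That 39% was measured at the 2-month post-treatment follow-up, among 19 men in both arms combined. It is not a fall across treatment weeks, is not reported as proportional to baseline, and the calculation would ignore the urn.
- **Binary outcomes.** The algebra is for the linear models. Two of the listed primary measures are proportions of men, and in a nonlinear model a main-effect covariate would change the interaction coefficient.

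None of this restores the adjustment to the slope test. The objections limit the claim to lost precision and exposure to chance imbalance.

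**Conclusion.** The point holds in limited form. As written, C.8.a.2 specifies no covariate-by-week term. On the natural reading, the two covariates leave the named test for standard drinks per week and heavy drinking days per week unchanged with complete data. With about 9% dropout the mean shift is 3% to 5% of a standard error, and the largest seen was 0.023 against 0.153 (15%).

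The potential gain is a rise in power at d = 0.45 from about 81% to 85-89%, if 10% to 20% of the slope variance is explained. The documents support no particular share, and it may be near zero on a log scale. The case is clearest for treatment goal, which is outside the urn and plausibly related to the rate of change. This is a worthwhile improvement to the model, not a fault in the validity of the test.

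**What to change.** In C.8.a.2, add pretreatment drinking by week and treatment goal by week to the linear mixed models for standard drinks per week and heavy drinking days per week, and keep the main effects. Use the pretreatment value of the same measure as the outcome, on the same scale, including any transformation. Make the change before unblinding.

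The cost is one sentence and two fixed effects per model, on data already collected. If the terms explain nothing, the loss is slight: in the complete-data simulation, with the covariance held fixed, the standard error went from 0.1539 to 0.1552, a rise of 0.8%, even under the large assumed imbalance. If the terms were intended all along, the section need only say so.
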